#### 11.2 Power Analysis

The primary aim of the proposed pilot is feasibility. We chose the sample size of 60 patients based on the feasibility of completing the project during the proposed timeframe and the ability to assess the preliminary efficacy of the intervention. In a pilot study, at least 30 patients are needed in each group to estimate a parameter.  Thus, the proposed sample size will provide us with preliminary data that can be used to determine the effect size and adequately power future trials. Based on our prior pilot study, with a sample size of 60, we would have >80% power to detect a clinically significant 7-point difference in satisfaction with sex (SD=8) between the two groups.

#### 11.3 Data Security

The research team is trained in protecting patient health information. All data will be saved in a password-protected document on Partners computers. Only the research team will have access to the document. Patient data and study identifiers will be kept in separate documents and information linking participants to the study will be kept in a different document that will also be password-protected. Paper consent forms and surveys will be stored in a locked office at Massachusetts General Hospital. All patient-reported data will be reported electronically using Research Electronic Data Capture, a tool for creating and managing online surveys (REDCap). Our research team has significant experience using REDCap and will design the surveys in a web browser, assisted by institutional information technology support. Based on preference and feasibility, participants will be offered either paper surveys or electronic reporting through REDCap on computer tablets provided by the RA at the time of consent. Participant information will be kept confidential throughout the study period.

#### 11.4 Quality Control

An RA will enter hard-copy surveys into REDCap and review all surveys once. Another RA will perform a quality check on 10% of the surveys. If an error is found, an additional 5% will be checked until no errors are found.

11.5 Study-Wide Data Handling: please see description above regarding data security. We only have questionnaire data that will be stored electronically through REDCap. Paper questionnaires will be stored in a locked cabinet by the study team.

## 12.0 Provisions to Monitor the Data to Ensure the Safety of Subjects:

This project does not pose more than minimal risk to study participants. We do not anticipate any risks to study participation. We have utilized the study questionnaires and conducted interviews in prior studies without any adverse events. If a participant becomes distressed due to their involvement in the study, both the PI and their oncology clinician will be notified. We will offer participants who remained distressed the opportunity to meet with the PI ([name]) or a psychologist ([name], a co-investigator).

## 13.0 Withdrawal of Subjects

Participants will be withdrawn without their consent if it is in their best interest, if the study procedures are demonstrated to be risky or ineffective, if any problem arises following study procedures, if issues arise with research funding, or any other unforeseen circumstance. Participants will be notified if they are removed from the study.

## 14.0 Risks to Subjects

Though the intervention involves topics of a sensitive nature, we do not anticipate risks to subjects other than the risk of breach of confidentiality. Participation in our pilot study was not associated with any negative outcomes. No adverse reactions are anticipated during the proposed study as a result of the study procedures.

While no adverse or unanticipated events are expected in this behavioral trial, any such events will be immediately reported to the IRB. There is a minimal chance of causing harm with this study. We have administered all the questionnaires to over 100 transplant recipients with no adverse events. While some

topics probed in the app and study assessments are sensitive in nature, no adverse or unanticipated events occurred in previous studies discussing these topics. Additionally, our research team has extensive experience conducting studies using psychoeducational apps on sensitive topics without any adverse events. Further, our research team has experience conducting qualitative patient interviews.

Should participants exhibit or express distress or anger, they will be reassured by the study staff that they need not answer any questions which they find upsetting. They will also be reminded that study participation is voluntary. If participants remain distressed, both the PI and the oncologist will be notified. Should several participants express distress over an individual item, the research team will review the questionnaire and contact the IRB to consider removing it from the study.

We will prevent breaches in confidentiality by keeping participant data on password protected Partners computers and in a locked office on MGH campus. Data logged online will be saved in password protected documents. Only study team will have access to the data.

## 15.0 Potential Benefits to Subjects

#### 15.1 Potential benefits

Participants may or may not experience improved sexual function through taking part in this study. Participants (regardless of their study group assignment) will have the opportunity to meet with a transplant clinician to conduct a brief evaluation and that might be helpful in identifying problems related to their sexual dysfunction that can be addressed.

#### 15.2 Participant compensation

Participants will not be compensated for their involvement.

## 16.0 Vulnerable Populations: Not Applicable

## 17.0 Community-Based Participatory Research: Not Applicable

## 18.0 Sharing of Results with Subjects

Given the nature of the population included in the study, it is not appropriate to proactively contact participants at the conclusion of this study. We anticipate that a proportion of our participants will relapse or die after completing the study. We do not wish to cause unnecessary distress to participants' family members by attempting to contact participants who have died. Therefore, we provide the research team contact information to each participant and encourage them to contact us if they would like to receive updates and information on the research findings.

## 19.0 Setting

The research team will recruit potential subjects in the MGH Cancer Center and Dana Farber Cancer Institute oncology clinics. Beth Israel Deaconess Medical Center patients will be recruited by clinician referral. Consent and a baseline demographics survey will take place in the clinic or over the phone, at the time of recruitment. Participants will attend their visit with a transplant clinician with expertise in sexual health in the MGH Transplant Oncology Clinic; this visit may occur in clinic or virtually via secure video-based conference. Participants randomly assigned to the mobile app will use the mobile app in the privacy of their homes. Research procedures will occur on an out-patient basis or will occur remotely.

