#### 3.2 Eligibility

#### 3.2.1 Inclusion Criteria

- 1. Adult patients (≥18 years) who underwent an autologous or allogeneic HCT at least 3 months prior to study enrollment.
- 2. Ability to speak English or able to complete questionnaires with assistance required from an interpreter or family member.
- 3. Positive screen for sexual dysfunction that is causing distress based on the NCCN survivorship guidelines.

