## 4.0 Study-Wide Number of Subjects: 60 patients

## 5.0 Study-Wide Recruitment Methods:

We will use the same successful screening, recruitment, and enrollment procedures from our prior pilot study. An RA and [name] will screen the weekly transplant clinic schedule to identify potentially eligible patients. The RA will then send an email to the treating oncology clinician to notify him or her that the patient is potentially eligible for study participation and inquire about any concerns regarding his or her study participation. If the treating clinician has any objections regarding the patient's participation, the RA will document the reasons and not approach those individuals. If there is no concern regarding study participation, the RA or the oncology clinician will screen the patient for sexual dysfunction at their next scheduled visit using the two-question approach based on the NCCN Survivorship Guidelines: 1) "do you have problems with sexual function?" and 2) "are these problems causing you distress?". The RA will then offer study participation for those who screen positive for sexual dysfunction causing stress. The RA will then review the study procedures and informed consent document and obtain written informed consent.

Alternatively, if a patient is unable to be approached in-person to determine primary eligibility due to external factors, such as a lack of clinic space, or patient time constraints, the study team may reach out to potential participants over the phone. Prior to initiating phone contact, the study team will contact the treating oncology clinician to assess if the clinician has any reservations about study staff contacting the patient. Study staff will call the potentially eligible patient using the recruitment and screening phone script (see verbal consent) to gauge interest and screen the patient to determine eligibility. Study staff will not call more than three times total. If unable to reach the patient, study staff will leave a voicemail with staff contact information (see voicemail script). If the patient expresses interest and screens in, the RA will conduct informed consent over the telephone. Alternatively, study staff may approach the

patient at their next clinic visit to review the study procedures and the informed consent document and obtain written informed consent.

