The study team will additionally have the option of providing study information to eligible patients via Patient Gateway, using a template with recommended language (Appendix L). Patients will be given a summary of the study and will be encouraged to contact the study team using provided contact information if interested in hearing more about the study.

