## 8.0 Study Endpoints

- 8.1 Primary endpoint: The primary endpoint of this pilot RCT is to assess the feasibility of the intervention. The proposed intervention app will be deemed feasible if at least 60% (95% CI +/- 12%) of eligible patients are enrolled in the study, and of those enrolled, at least 60% engage with at least 70% of the intervention modules. Modules engagement will be captured by the app.
- 8.2 Secondary endpoints:
  - Compare patient-reported global satisfaction with sex (PROMIS Sexual Function and Satisfaction Measure) scores at 8 weeks between the study groups
  - Compare patient-reported interest in sexual activity (PROMIS Sexual Function and Satisfaction Measure Interest in sexual activity domain) scores at 8 weeks between the study groups
  - Compare patient-reported global satisfaction with sex (PROMIS Sexual Function and Satisfaction Measure Global satisfaction with sex domain) at 12 weeks between the study groups
  - Compare patient-reported interest in sexual activity (PROMIS Sexual Function and Satisfaction Measure Interest in sexual activity domain) at 12 weeks between the study groups
  - Compare patient-reported orgasm (PROMIS Sexual Function and Satisfaction Measure Orgasm domain) at 8 weeks and 12 weeks between the study groups
  - For males: compare patient-reported erectile function (PROMIS Sexual Function and Satisfaction Measure Erectile function domain) at 8 and 12 weeks between the study groups

- For females: compare patient-reported lubrication and vaginal comfort (PROMIS Sexual Function and Satisfaction Measure lubrication and vaginal comfort domains) at 8 and 12 weeks between the study groups
- Compare patient reported QOL (FACT-BMT) at 8 and 12 weeks between the study groups
- Compare patient reported anxiety and depression symptoms (HADS) at 8 and 12 weeks between the study groups

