#### 22.3 Identifying Potential Subjects

Potential subjects will be identified by screening the transplant clinic schedule at Massachusetts General Hospital and Dana Farber Cancer Institute. Beth Israel Deaconess Medical Center patients will be recruited by clinician referral. A trained RA will further determine eligibility by evaluating potential subjects' medical records. The RA will then reach out to the patient's oncology clinician to determine if the clinician believes participation is appropriate. The last screening test will be the two questions in the NCCN guidelines used to determine the presence of sexual dysfunction causing distress.

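### The 60% enrolment criterion pools staff-screened patients with referral and opt-in entrants whose non-enrolled counterparts are largely unseen, so the proportion is likely, though not certainly, biased upward

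*Combined protocol and SAP*

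**What the plan says.** Sections 8.1 and 11.1 set two conditions for feasibility. The first is that "at least 60% (95% CI +/- 12%) of eligible patients are enrolled in the study". The second is that at least 60% of those enrolled engage with at least 70% of the modules. Neither section defines the denominator of the first condition, limits it to a recruitment route, or asks for results by route.

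Eligibility includes a "Positive screen for sexual dysfunction that is causing distress based on the NCCN survivorship guidelines" (3.2.1). Section 22.3 places that step at the end: "The last screening test will be the two questions in the NCCN guidelines used to determine the presence of sexual dysfunction causing distress".

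Patients can reach that screen in different ways:

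- **Clinic schedule, MGH and DFCI.** "Potential subjects will be identified by screening the transplant clinic schedule at Massachusetts General Hospital and Dana Farber Cancer Institute" (22.3). Unless the treating clinician objects, the research assistant or the oncology clinician asks the two questions at the next visit (3.1, 5.0). If an in-person approach is not possible, staff may telephone; "Study staff will not call more than three times total" (5.0).
- **Referral, BIDMC.** "Beth Israel Deaconess Medical Center patients will be recruited by clinician referral" (19.0, repeated in 22.1 and 22.3). No list of patients who were not referred is described.
- **Patient portal.** "The study team will additionally have the option of providing study information to eligible patients via Patient Gateway" (5.0). Recipients are invited to get in touch if they want to hear more. No follow-up or logging rule is given.

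Section 23.0 draws the 60 participants from all three institutions together.

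**The concern.** An enrolment proportion measures uptake only if enrolled and non-enrolled eligible patients are both seen. In the schedule route they are, once screened: a patient who screens positive and declines is on record. In the other two routes a patient is partly selected for willingness before anyone can establish eligibility. A BIDMC patient reaches the screen only if a clinician refers them, and a Gateway recipient only by replying. Those not referred, and those who do not reply, have no completed screen, so on the inclusion criterion they cannot be shown to be eligible. The enrolments from these routes still enter the numerator.

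At stake is one of the two primary criteria. If uptake in the staff-screened route is somewhat below 60%, the pooled figure could be reported as meeting the threshold because of how some patients arrived.

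**Working it through.** **1. The plan's own figure.** The Wald 95% half-width at 60% is 1.96 × √(0.6 × 0.4 / n). With n = 60 it is 12.4 points, with n = 64 it is 12.0, and with n = 66 it is 11.8. The stated ±12% therefore corresponds to a denominator of about 60 to 66. If 60 enrolments were exactly 60% of those eligible, the denominator would be 60 / 0.6 = 100 and the half-width 9.6 points.

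**2. Inputs.** From the documents: 60 enrolments (23.0), the 60% threshold (8.1), and pilot uptake of 47/50 = 94.0% among screen-positive patients (2.2). Not in the documents, so assumed over a range:

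- m, the number of the 60 enrolled by referral or opt-in: 6 to 24.
- p, uptake in the staff-screened route: 50% or 55%, with the pilot's 94% as a check.
- c, apparent uptake in the referral and opt-in routes when unseen patients are not counted: 90% to 100%.

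**3. Formula.** Pooled proportion = 60 / [(60 − m)/p + m/c].

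Example with p = 0.55, m = 12, c = 1.0: 48/0.55 = 87.27; 87.27 + 12 = 99.27; 60/99.27 = 60.4%. With c = 0.9: 87.27 + 13.33 = 100.61; 60/100.61 = 59.6%.

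| m of 60 | p = 55%, c = 90% to 100% | p = 50%, c = 90% to 100% |
|---|---|---|
| 6 | 57.2% to 57.6% | 52.3% to 52.6% |
| 12 | 59.6% to 60.4% | 54.9% to 55.6% |
| 18 | 62.3% to 63.6% | 57.7% to 58.8% |
| 24 | 65.1% to 67.1% | 60.8% to 62.5% |

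**4. Where the verdict flips.** The pooled figure reaches 60% when (60 − m)/p + m/c ≤ 100. With c = 1.0 this needs m ≥ (60/p − 100)/(1/p − 1). For p = 0.55 that is 9.09/0.818 = 11.1, so 12 patients. For p = 0.50 it is 20/1 = 20 patients.

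**5. At the pilot's uptake.** With p = 0.94 and m = 18: 42/0.94 = 44.68. Then 60/(44.68 + 20) = 92.8% for c = 0.9, and 60/(44.68 + 18) = 95.7% for c = 1.0. The shift is under 2 points in either direction, and the criterion is met by a wide margin.

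**6. The opposite counting rule.** Suppose all 12 entrants came through Gateway and every silent recipient were counted as eligible, with uptake in that route of 20% to 50% (assumed). With p = 0.55 the pooled figure is 60/(87.27 + 60) = 40.7% to 60/(87.27 + 24) = 53.9%. The same recruitment could then read 60.4% or well below 60%, depending on a rule that the plan does not state.

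**The case against.** A reader might infer that patients who stay silent never count as eligible, so that upward bias is certain. The documents do not say so. Section 5.0 describes the portal option as going to patients already called eligible: "The study team will additionally have the option of providing study information to eligible patients via Patient Gateway". On that wording silent recipients could be counted, which would lower the proportion. This objection stands, and it limits the claim about direction to likely.

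A reader might also treat all the less direct routes alike. That does not hold either:

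- A referred BIDMC patient who screens positive and declines is eligible and not enrolled, and does count. The unseen group there is the patients who are not referred.
- The telephone route is started by staff and does not preselect willing patients. Those not reached have unknown eligibility, and with 33.1% (50/151) screening positive in the pilot, most would not be eligible. Leaving them out follows the endpoint as written.

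The schedule route is not a perfect benchmark. Patients whose clinician objects are not approached and so are not screened. That gap remains under any restriction to MGH and DFCI and needs reporting.

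On size, every route share and uptake in the illustration is assumed, and the one documented uptake, 94%, leaves the verdict unchanged. That is fair, with a reservation: the pilot offered nurse-practitioner visits in a pre-post design, whereas this trial randomises between the app and enhanced standard care. By setting its threshold at 60%, the plan treats lower uptake as possible.

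Finally, enrolment across all routes in use is a legitimate feasibility target. But the plan does not say whom it would count in that target's denominator for the referral and portal routes.

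**Conclusion.** The point holds in a limited form. The enrolment criterion mixes a route in which screened, eligible non-enrollees are seen with two routes in which entrants are partly selected for willingness and their non-enrolled counterparts are largely unseen. The pooled proportion is likely to be too high, but the documents do not make this certain.

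Under the stated assumptions, with 55% uptake among staff-screened patients, the upward shift runs from about 2 points (6 of 60 by referral or opt-in) to about 12 points (24 of 60). It takes about 12 of 60 to bring 55% to the threshold, and at least 20 of 60 to bring 50% there. If staff-screened uptake is itself 60% or more, the conclusion does not depend on this upward shift.

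It would be too strong to infer that the trial will wrongly be declared feasible. The route shares are unknown, the pilot's uptake was far above the threshold, and the separate module-engagement condition must also be met.

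**What to change.** In 8.1 and 11.1:

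- Test the 60% criterion among MGH and DFCI patients identified from the clinic schedule and screened through staff-initiated contact, in clinic or by telephone. The denominator is every such patient who screens positive and meets the other criteria, whether or not they later decline or are lost.
- Assign each patient a single route by how they came to be screened. This settles the case of a patient who is on a clinic schedule and also receives a portal message.
- Report referral and Gateway enrolments separately. They remain in the randomised 60.
- Report how many patients were not approached because a clinician objected, and how many were contacted but never completed the screen.
- Restate the expected confidence-interval half-width for this denominator.

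Recruitment and randomisation are unchanged. The cost is a route column in the screening log and a short addition to each section. The denominator becomes smaller: if 48 of the 60 came by the schedule route at 60% uptake, it would be 48/0.6 = 80 rather than 100, and the half-width 1.96 × √(0.24/80) = 10.7 points rather than 9.6. The criterion would also no longer describe the referral site, so feasibility there would rest on the separate report.

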#### 20.0 Resources Available

Team Qualifications

[name], [name] and [name] (co-investigator) have the experience to ensure the success of the proposed project. [name] has led several trials studying interventions to improve the quality of life and care of patients with cancer. Our investigative team has substantial expertise in developing and testing supportive care interventions, adapting these interventions to mobile applications, and addressing sexual health concerns in cancer survivors. Our team additionally has extensive experience in conducting qualitative interviews with patients.

The study team will train the RA to identify potentially eligible patients, approach patients for study participation, obtain informed consent, and conduct qualitative interviews and provide patients randomized to the intervention with a comprehensive tutorial regarding how to use the app. Our research team has extensive experience training RA to work with medically ill cancer population, recognizing participants' burden and distress, conducting qualitative patient interviews, as well as educating participants on the use of mobile apps. We will utilize similar training procedures to our prior studies.

#### 20.1 Other Resources

The MGH Transplant Program performs approximately 200 new transplants per year and cares for over 700 HCT survivors. Therefore, we are confident in our ability to meet accrual goals.

The research team will devote as much time as is needed to conducting and completing the research. Our facilities are located on the Massachusetts General Hospital main campus within walking distance of the transplant clinic. Our research team uses Partners computers and have access to Partners resources to undertake this endeavor.

Though we do not anticipate adverse reactions as a result of participation in this study, participants who express distress will have access to psychologist [name].

The research team will have access to the protocol and documents regarding research procedures. Responsibilities will be communicated in a timely manner through weekly team meetings and email.

